# Grant Information:

IRB Approval: This project is not currently IRB approved

Proposed Starting Date of Research: February/March 2016

Anticipated Date of Completion: August/September 2016

Timeline of activities: Estimate 2-3 months for IRB approval. Once approved the study will likely take 2-3 months, possibly sooner given the volume of patients with atopic flares (especially during winter months) seen at the pediatric dermatology clinic. After data collection, 1-2 months will be required for statistical analysis. Overall, we project to have research completed and data analyzed by August/September of 2016

## **Overall goals and background**

Atopic Dermatitis (AD) is a common skin condition affecting 10-20% of children in the United States. Atopic dermatitis is associated with chronic pruritus and inflammation leading to significant discomfort, stress and social stigma. Wet wraps (corticosteroid contained in a vehicle wrapped in wet dressings) have been used for many years and are an effective means of improving moderate to severe atopic dermatitis. A wet wrap's efficacy is a product of a corticosteroid's activity at the site of action, as well as patient compliance. Wet wraps can be messy and difficult to use for patients and families and has been associated with variable adherence. Interestingly, little research has been done regarding wet wrap comparable efficacy and patient tolerability. Recent studies have shown that wet wraps with topical steroids are superior to emollients alone. However, there are no studies comparing different vehicles for topical steroids when used for this treatment.

The purpose of this study is to

1. Compare efficacy of 0.1% triamcinolone containing wet wrap as an ointment or as a cream formulation in patients with moderate to severe atopic dermatitis

2. The relative patient/subject acceptance and adherence will also be compared between the two wet wrap types

# Hypothesis

Significant controversy exists on the optimal vehicle for wet wraps. Some advocate for cream (oil in water) formulations because they are hydrophilic and therefore may be absorbed better in the aqueous environment of a wet dressing. Others prefer ointments (water in oil) because they are more potent than creams. We hypothesize that the overall difference will be negligible and that patient preference should be the largest factor in deciding which to use. Many patients prefer creams because they are lighter and more elegant while others prefer the thickness of ointments.

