instructions to apply one steroid formulation to the right extremity and the other to the left. In this manner the providers will be blinded to treatment modality during the follow-up visit. Only the research coordinator will have access to the envelope code key. An additional handout will also be provided to reinforce appropriate treatment technique. After several days (3-5) the patient will return to the dermatology clinic for a nurse visit and evaluation of any improvement of the affected areas as well as comparison of improvement of the right and left extremities. The physician investigator will examine the patient and measure improvement using the IGA. Detailed photos of the affected areas will also be taken. After a certain number of patients have enrolled in the study and completed it, the de-identified data will be examined by a statistician for comparison. Other studies evaluating the effectiveness of wet wraps have commonly had 40-50 patients enrolled which will likely be the target of this study. The statistician will compare the IGA before and after treatment on each side to allow for interpretation of the data. Stratification of data may include ages and/or severity (moderate vs severe).

Patient Oriented Eczema Measure (POEM) and/or a Quality of Life (QoL) index will also be provided before and after treatment in order to determine the patient's point of view regarding their management using validated tools. They will also be asked their opinion regarding if one side was better controlled than the other, if at all, as well as their personal preference for treatment of choice.

Compliance will be determined by weighing the medication before and after each visit and a medication calendar.

The participating clinicians, including myself, will be performing the IGA before and after treatment. I will also be responsible for data collection as well as help with statistical analysis under the mentorship of [name] and possibly a statistician if needed.

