## **Relevance to Professional Career**

The dermatology service recently had an inpatient with erythroderma who was not responding to topical steroids used with wet dressings. In our discussion during grand rounds, someone suggested that switching from a cream to ointment may help. We did a quick literature search and could not find any relevant insight. Given that atopic dermatitis makes up a significant portion of the diseases in pediatric patients seen by dermatologists, I would like to elucidate whether one formulation is superior to another for this often used treatment. Although I have no research experience with topical steroids or eczema, I have conducted dermatologic research through surveys in the past. I hope the information acquired from this study will fill the knowledge gap that currently exists and will provide an opportunity to improve patient care. If there is truly no clinical difference between topical steroid creams and ointments used in wet wraps, then patient preference will play the largest role in deciding which to use. One of my professional goals is to continue to be involved in research and this experience will help me to build a foundation for future investigations.

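### The plan hypothesizes a negligible cream-ointment difference, but states no margin, interval or other criterion for concluding it

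*Combined protocol and SAP*

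**What the plan says.** The plan asks two kinds of question about efficacy.

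- **A two-sided question.** The first stated purpose, in Overall goals and background, is "Compare efficacy of 0.1% triamcinolone containing wet wrap as an ointment or as a cream formulation". Relevance to Professional Career adds "I would like to elucidate whether one formulation is superior to another for this often used treatment".
- **A hypothesis of no important difference.** The Hypothesis section reads: "We hypothesize that the overall difference will be negligible and that patient preference should be the largest factor in deciding which to use". Relevance to Professional Career attaches the same practical consequence to the condition "If there is truly no clinical difference between topical steroid creams and ointments used in wet wraps".

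The Methods section contains the analysis text. On the IGA it says: "The statistician will compare the IGA before and after treatment on each side to allow for interpretation of the data". It also foresees "comparison of improvement of the right and left extremities" at the return visit, and it asks patients whether one side was better controlled. The target of 40-50 patients is taken from the size of other wet-wrap studies. The plan gives no test, significance level, power, SD, smallest important difference, margin or confidence interval.

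**The concern.** An ordinary comparison can answer the two-sided question if it finds a difference. The hypothesis is of the other kind. To conclude that a difference is negligible, one must show that the data exclude differences large enough to matter, and that requires saying beforehand how large that is. The plan does not say.

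The practice message, that preference should choose the vehicle, rests on this conclusion. Followed as written, the plan could reach it only by inference from not finding a difference, or by judging what counts as negligible after seeing the result. In the first case, the chance of overlooking a difference that matters would depend on an SD that the plan does not give.

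**Working it through.** **1. Side by side.** The Hypothesis section expects that "the overall difference will be negligible". Each planned comparison was checked for a criterion that could support this.

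| Planned comparison | Section | Criterion for 'negligible' |
|---|---|---|
| IGA before and after, each side | Methods | none stated |
| Improvement, right against left | Methods | none stated |
| Patient's opinion of the two sides, and preference | Methods | none stated |
| POEM and/or quality-of-life index | Methods | none stated |
| Acceptance and adherence | Overall goals and background | none stated |

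**2. The plan's own figure.** The 40-50 target cannot be reproduced, because it has no significance level, power, SD, effect size or margin behind it. It serves below only as the number of evaluable pairs.

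**3. What a non-significant result would be worth.** Everything except n is assumed: a two-sided 5% paired t test, normally distributed differences, IGA scored in grades (Methods says only that the scale is numeric), and SD = standard deviation of the within-child cream-minus-ointment difference in IGA change.

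With true difference d, the test statistic follows a noncentral t distribution with n − 1 degrees of freedom and noncentrality δ = d√n / SD. The chance of non-significance is P(−c < T < c), where c = 2.023 for n = 40 and 2.010 for n = 50.

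At SD 1.0:
- d = 0.5: δ = 0.5 × √40 = 3.16 and 0.5 × √50 = 3.54, giving 13.1% and 6.6%.
- d = 0.3: δ = 1.90 and 2.12, giving 54% and 45%.

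Over a range of SDs (n = 40 / n = 50):

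| SD | d = 0.5 | d = 0.3 |
|---|---|---|
| 0.5 | 0.0% / 0.0% | 4.1% / 1.4% |
| 0.6 | 0.1% / 0.0% | 13.1% / 6.6% |
| 0.8 | 2.9% / 0.9% | 36.2% / 26.1% |
| 1.0 | 13.1% / 6.6% | 54% / 45% |
| 1.2 | 27.1% / 17.7% | 66.2% / 59.0% |

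The 0.5-grade risk passes 5% only when the SD exceeds about 0.86 / 0.96. The 0.3-grade risk does so above about 0.51 / 0.58.

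**4. What a margin rule would do.** The rule concludes 'negligible' only if the paired 90% CI lies wholly inside ±M, which is the same as two one-sided 5% tests. Its properties were found by integrating over the distribution of the sample SD.

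- *True difference equal to M:* the rule wrongly concludes 'negligible' at most 5% of the time at every SD examined (5.0% for M = 0.5; 0.9-5.0% for M = 0.3).
- *True difference inside M:* there is no such limit. With M = 0.5 and a true difference of 0.3, the rule concludes 'negligible' about 80% / 87% of the time at SD 0.5 and 46% / 54% at SD 0.8.
- *True difference 0 (power):*

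| SD | M = 0.5 | M = 0.3 |
|---|---|---|
| 0.6 | 100% / 100% | 85.6% / 93.4% |
| 0.8 | 97.5% / 99.3% | 50.7% / 66.8% |
| 1.0 | 85.6% / 93.4% | 18.3% / 34.5% |
| 1.2 | 65.5% / 79.2% | 3.0% / 10.2% |

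Power is at least 80% for SDs up to 1.06 / 1.19 with M = 0.5, and up to about 0.64 / 0.71 with M = 0.3.

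**The case against.** **The analysis is unspecified rather than incapable.** A paired difference with a confidence interval would fit the wording of the Methods section. This stands, and so the point is limited to the absence of a stated criterion. It does not say that the planned data could never support the hypothesis.

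**The misuse is hypothetical.** A reader might infer that the investigators will take a non-significant result as proof of equivalence. The documents do not support that: they plan no significance test, and nowhere say that non-significance will be read as 'negligible'. The sentence about no clinical difference is a conditional remark in a career statement and not a decision rule. The percentages above show what such a reading would risk and do not describe the plan's own procedure.

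**The risk may be small.** For a true 0.5-grade difference it is 3% or lower at SD 0.8 or less. This stands: below an SD of about 0.86 / 0.96, a 0.5-grade margin gives no more protection against that difference than non-significance would. The risk is large only with a larger SD or a smaller important difference, and the documents give neither.

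**A reader might also infer that 40-50 patients is too few.** That cannot be shown. Depending on margin and SD, the same number gives power close to 100% or close to none.

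**This is a short proposal written before IRB approval.** True, but it is also the only analysis plan. Because it is prospective, a criterion can still be set before any data are seen. The gap is also narrower than general missing detail, since it concerns the conclusion the study expects to draw.

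**Conclusion.** The concern holds in this form: the plan hypothesizes a negligible difference and ties a practice conclusion to it, but states no criterion by which any of its comparisons could lead there. This rests on the text alone and needs no assumption.

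The size is illustrative. At an assumed SD of 1.0 with 40/50 pairs, non-significance would miss a true 0.5-grade difference 13%/7% of the time and a true 0.3-grade difference 54%/45%. At SD 0.8 or less the 0.5-grade figure is 3% or lower. The test, the SD, the important difference and the grading of the IGA are all assumed, so no single magnitude can be attributed to this plan.

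It should be fixed before enrolment. It does not invalidate the comparison itself, which can still be estimated and can still answer the superiority question.

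**What to change.** In the Methods section, state that:

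1. The primary efficacy result is the within-child cream-minus-ointment difference in IGA change, reported with its paired 95% CI. That interval answers the superiority question.
2. 'Negligible' or 'no clinical difference' is concluded only if the paired 90% CI lies wholly inside a margin that the investigators set and justify before enrolment, in units of the IGA version used.
3. If the 90% CI is inside the margin but the 95% CI excludes zero, the result is reported as a difference smaller than the margin.
4. If no margin is set, the difference is reported with its 95% CI and no conclusion of 'negligible' is drawn.

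**Cost.** This is a short paragraph, with no new data or visits. The investigators must fix the IGA version and justify a margin by clinical judgement, and the margin may lead them to revisit the 40-50 target. Option 4 avoids the margin. The 5% limit on false 'negligible' conclusions applies only to true differences at or beyond the margin, so protection depends on the margin chosen. The result may be inconclusive if the SD is large or the margin tight.

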## **Methodology and Rationale**

### Inclusion Criteria

- 1. Patients between the ages of 3-17 experiencing a symmetric, bilateral flare of atopic dermatitis
- 2. The flares must reach a certain threshold for inclusion based on the investigator's global assessment scale

## Exclusion Criteria

- 1. Systemic infection or bacterial skin infections
- 2. Eczema herpeticum
- 3. Evidence of suppression of the Hypothalamic-Pituitary-Adrenal axis
- 4. Non-English or Non-Spanish speaking

#### **Methods**

Patients and/or parents will be asked to sign an informed consent authorizing their participation in the study. All information will be de-identified to protect the patient's privacy.

In this study, we will examine the effectiveness of wet wraps with topical steroids in different formulations for patients with a history of atopic dermatitis who are experiencing an acute flare. A validated clinical tool such Investigator's Global Assessment (IGA) will be used in order to assess severity of the condition as well as demonstrate the appropriateness of using wet wrap therapy as a treatment modality. IGA will measure intensity of the atopic dermatitis regarding erythema, lichenification, swelling and excoriation as well as subjective symptoms of the patient on a numeric scale. The treating clinician will be asked to rate their assessment before and after therapy.

Patients will be asked to apply a topical steroid in a cream formulation to one extremity and then apply the same topical steroid in an ointment formulation to the other using the wet wrap technique. One of the investigators or nursing staff will provide detailed instructions to the patient and parents on how to perform the wet dressing (this is already routinely done for patients initiating wet wrap therapy in the pediatric dermatology clinic). Patients will also be given a sealed and coded envelope containing

instructions to apply one steroid formulation to the right extremity and the other to the left. In this manner the providers will be blinded to treatment modality during the follow-up visit. Only the research coordinator will have access to the envelope code key. An additional handout will also be provided to reinforce appropriate treatment technique. After several days (3-5) the patient will return to the dermatology clinic for a nurse visit and evaluation of any improvement of the affected areas as well as comparison of improvement of the right and left extremities. The physician investigator will examine the patient and measure improvement using the IGA. Detailed photos of the affected areas will also be taken. After a certain number of patients have enrolled in the study and completed it, the de-identified data will be examined by a statistician for comparison. Other studies evaluating the effectiveness of wet wraps have commonly had 40-50 patients enrolled which will likely be the target of this study. The statistician will compare the IGA before and after treatment on each side to allow for interpretation of the data. Stratification of data may include ages and/or severity (moderate vs severe).

Patient Oriented Eczema Measure (POEM) and/or a Quality of Life (QoL) index will also be provided before and after treatment in order to determine the patient's point of view regarding their management using validated tools. They will also be asked their opinion regarding if one side was better controlled than the other, if at all, as well as their personal preference for treatment of choice.

Compliance will be determined by weighing the medication before and after each visit and a medication calendar.

The participating clinicians, including myself, will be performing the IGA before and after treatment. I will also be responsible for data collection as well as help with statistical analysis under the mentorship of [name] and possibly a statistician if needed.

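### The per-side before-after IGA comparison can show improvement without any treatment effect, and it is not the cream-versus-ointment comparison the study sets out to make

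*Combined protocol and SAP*

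**What the plan says.** **Entry.** Inclusion Criteria admit "Patients between the ages of 3-17 experiencing a symmetric, bilateral flare of atopic dermatitis" and add that "The flares must reach a certain threshold for inclusion based on the investigator's global assessment scale". No cut-off is given.

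**Treatment.** Under Methods, the task given to each child reads: "apply a topical steroid in a cream formulation to one extremity and then apply the same topical steroid in an ointment formulation to the other". Neither study limb is left untreated or given emollient or vehicle alone, and there is no separate control group.

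**Aim.** The first purpose, in Overall goals and background, is comparative: "Compare efficacy of 0.1% triamcinolone containing wet wrap as an ointment or as a cream formulation". It sets that comparison "in patients with moderate to severe atopic dermatitis". The Methods section uses broader wording: "we will examine the effectiveness of wet wraps with topical steroids in different formulations".

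**Analysis.** The plan's one statement of a statistical comparison is: "The statistician will compare the IGA before and after treatment on each side to allow for interpretation of the data". The same section describes a follow-up visit at 3-5 days at which improvement on the right and left is compared, but it does not make that contrast the statistical analysis. POEM and/or a quality-of-life index are also completed before and after treatment. The target is 40-50 patients.

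**The concern.** The scale that decides entry is also the outcome. A child selected because today's IGA is high will on average score lower a few days later, partly because the entry score includes a temporary excess and partly because flares subside. Both limbs are actively treated, so nothing in the design separates that fall from a treatment effect.

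Two consequences follow.

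- A before-after comparison on each side cannot support a statement about the effectiveness of wet wraps. POEM and quality of life are exposed in the same way. As described they are also not side-specific, so their change has no within-child comparator.
- Two per-side comparisons do not add up to a comparison of the vehicles. The first purpose needs the difference between sides, and the analysis sentence does not specify it.

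This bears on the study's own hypothesis of a negligible difference. If both sides improve equally, the data cannot distinguish two products that work from two flares that subsided.

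**Working it through.** **The plan's own figure.** The target of 40-50 patients is taken from the size of other wet-wrap studies. No alpha, power, effect size or SD is given, so it cannot be reproduced. It is used here only as the sample size.

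**Inputs.**
- From the documents: entry on a flare above an IGA threshold; both study limbs active; IGA before and after on each side; follow-up at 3-5 days; n = 40 to 50.
- Assumed, because the documents do not say: an entry cut c of 0 to 1 SD above mean severity; a baseline-to-follow-up correlation r of 0.5 to 0.95; a paired t-test on each side at the two-sided 5% level; normally distributed severity; zero treatment effect.

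**Formulas (in SD units of IGA).**
- Mean excess at entry: λ = φ(c) / (1 − Φ(c)), which is 0.798 at c = 0 and 1.525 at c = 1.
- Expected fall with no treatment effect: (1 − r)λ.
- Variance of change: (1 − r)²(1 + cλ − λ²) + (1 − r²).
- Chance of a significant improvement: upper tail of the noncentral t with n − 1 degrees of freedom and noncentrality fall × √n / SD of change. The critical value at n = 40 is 2.023.

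**Worked case, r = 0.7, c = 0, n = 40.** Fall = 0.3 × 0.798 = 0.239. Variance = 0.09 × 0.363 + 0.51 = 0.543, so SD = 0.737. Noncentrality = 0.239 × 6.325 / 0.737 = 2.05. The chance of significance is 52%. At c = 1 the fall is 0.458, the SD 0.727 and the noncentrality 3.98, giving 97%.

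**Results at n = 40, over c = 0 to 1.**

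| r | Expected fall (SD) | Chance of a significant 'improvement' |
|---|---|---|
| 0.5 | 0.40-0.76 | 77% to nearly 100% |
| 0.7 | 0.24-0.46 | 52-97% |
| 0.8 | 0.16-0.31 | 36-87% |
| 0.9 | 0.08-0.15 | 20-57% |
| 0.95 | 0.04-0.08 | 12-32% |

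At n = 50 the chances are higher, for example 24-68% at r = 0.9 and 14-39% at r = 0.95. The comparator is a two-sided 5% level, of which 2.5% lies in the direction of improvement.

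**Check on a discrete scale.** A simulation used an integer 0-4 IGA with no treatment effect. It assumed a long-run mean of 2 and SD of 1, entry at 3 or more on both limbs, and a between-limb correlation of 0.9.
- Mean change was −0.43 points at r = 0.7 (−0.42 at n = 50) and −0.18 at r = 0.9.
- A false improvement on a side occurred in 94-97% of trials at r = 0.7 and 51-62% at r = 0.9, for n = 40 to 50.
- The left-right difference in change was significant in 4-6% of trials, about the nominal rate.

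The artefact therefore lies in the per-side comparison and cancels in the within-child contrast. Neither calculation models natural resolution of the flare, nor the assessors' knowledge that both limbs were treated. Both would be expected to add to the apparent improvement.

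**The case against.** The strongest reply is that this is a comparative study. Both stated purposes, the hypothesis and the career-relevance section concern cream against ointment. The background treats wet wraps as already shown to be effective, and the Methods phrase on effectiveness ends by referring to different formulations. The analysis sentence names no test, null hypothesis or p-value. It can be read as computing each side's change so that the sides can be compared, which fits the right-left evaluation at the follow-up visit.

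Most of this stands. A reader might infer that the plan commits the investigators to testing each side against zero and announcing that wet wraps work. The documents do not go that far: such a test is one open reading, and no endpoint or hypothesis concerns effectiveness against no treatment. A reader might also infer that false improvement is near certain. That is not shown either. Over 3-5 days the correlation could be high, and the chance then falls to the lower rows of the table. Two further inferences lack support: that clinicians over-score at entry so that children qualify, and that every limb is treated. Methods describes two study extremities and is silent on other areas.

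What remains is that the analysis sentence, as written, specifies a comparison within each side and leaves the comparison between sides unspecified. Nothing limits before-after change to description. Prior evidence may support effectiveness, but this study's before-after change cannot add to it.

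**Conclusion.** The point holds in limited form. Threshold entry during a flare, with both study limbs actively treated, biases the per-side before-after change towards improvement. The direction follows from the design, but the size is uncertain. Under the assumed cut and a paired t-test at n = 40, the chance of a false improvement is 52-97% at r = 0.7, 20-57% at r = 0.9 and 12-32% at r = 0.95. Even the most favourable case shown, 12%, is more than twice the nominal 5%.

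A reader might go further and conclude that the study's main comparison is compromised. It is not, by this mechanism: both limbs share the selection and the time course, and the cream-minus-ointment contrast kept its nominal error rate in the simulation. The fault is that the stated analysis is not that contrast, and that the Methods wording invites a claim the design cannot carry. This should be corrected before the study starts.

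**What to change.** **Methods, statement of aim.** Replace the wording on examining effectiveness with a statement that the study compares cream with ointment under wet wraps.

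**Methods, analysis sentence.** Replace the per-side before-after comparison with text such as: 'The primary analysis is the paired within-child difference (cream minus ointment) in IGA change from baseline to follow-up, and conclusions rest on it. Per-side IGA change and POEM and quality-of-life change are reported as descriptive summaries, are not tested against zero and are not interpreted as effectiveness of wet wraps. Equal improvement on both sides is not taken to show that both products work.'

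**Cost.** A few sentences, with no change to design, sample size or data collection. The study gives up an absolute-effectiveness statement that it could not have supported. The rewording does not itself show that either product works. That would have to come from outside evidence or a concurrent control.

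### The coded envelope hides the allocation code but not the product on the skin, so the stated provider blind is not secured when the physician rates the two limbs

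*Combined protocol and SAP*

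**What the plan says.** The blinding arrangement is in the Methods section of the combined protocol and SAP. The comparison is within the child: "Patients will be asked to apply a topical steroid in a cream formulation to one extremity", with the ointment form of the same steroid on the other limb. The allocation reaches the family on paper, in a sealed envelope that carries a code. Its contents are described as "instructions to apply one steroid formulation to the right extremity and the other to the left". The next sentence draws the conclusion: "In this manner the providers will be blinded to treatment modality during the follow-up visit". One supporting measure follows: "Only the research coordinator will have access to the envelope code key".

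At the 3-5 day visit, which is set up as a nurse visit with a physician examination, right and left are compared: "The physician investigator will examine the patient and measure improvement using the IGA. Detailed photos of the affected areas will also be taken". The IGA before and after treatment on each side is what the statistician is to compare. It is the only efficacy comparison the plan states, although the plan does not formally name a primary endpoint.

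The Hypothesis section describes the two vehicles as different materials. On cream: "Some advocate for cream (oil in water) formulations because they are hydrophilic". Ointment is given as water in oil. On feel: "Many patients prefer creams because they are lighter and more elegant while others prefer the thickness of ointments".

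**The concern.** The opening words of the blinding sentence attribute the provider blind to the envelope. The envelope and key prevent a provider from looking up the allocation. They cannot prevent a provider from recognising it on the limb. The physician sees both limbs of the same child at one visit, which is the setting in which a difference in greasiness or texture would be easiest to notice.

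The IGA is a clinician's judgement. A rater who recognises the vehicle could, without intending to, favour the vehicle they believe in and create a difference. Equally, they could score towards the plan's stated expectation of a negligible difference and hide a real one. The within-child design removes differences between children but not this bias, because the bias acts on the difference between the limbs. One of the raters, the applicant, also collects the data and helps with the analysis, so a rater outside the rest of the study is not available as a backstop. Neither photographs nor scores can be corrected afterwards if product was present when they were taken.

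**Working it through.** The plan gives no figure for this point, so there is nothing to reproduce. The check is of the text, followed by two illustrations.

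**Text, set side by side**

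| Question | What the plan gives |
|---|---|
| What produces the blind? | Sealed, coded envelope; key held by the coordinator (Methods) |
| Do the products differ physically? | Yes: oil in water and lighter, against water in oil and thicker (Hypothesis) |
| Does the rater see both products' limbs? | Yes, in person, with right compared with left (Methods) |
| Interval from last application to the visit | Not stated |
| Cleaning or other preparation of the limbs | Not stated |
| Check of whether the blind held | Not stated |
| Residue on the limb | Not mentioned |

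The first six rows support the statement that the blind can fail at the examination. The last row means that the physical cue itself is inferred.

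**Illustration 1: shift in the mean IGA difference**

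Assume that the rater recognises the ointment limb in a fraction p of children and then shades the limb difference by 0.5 IGA point. Both values are assumptions. If all shading goes one way, the bias is 0.5 × p:
- p = 0.2: 0.5 × 0.2 = 0.10
- p = 0.7: 0.5 × 0.7 = 0.35

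If a share q of the shaded ratings favours ointment and 1 − q favours cream, the bias is 0.5 × p × (2q − 1). This is zero at q = 0.5. So 0.5p is an upper bound for the assumed half-point shading, reached only when every rater leans the same way.

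**Illustration 2: false-positive rate**

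Assume a paired two-sided z test at 5%, no true vehicle difference, and a consistent bias of b standard deviations of the within-child difference. The number of children n is the plan's 40-50 target. The rejection rate is Φ(b√n − 1.96) + Φ(−b√n − 1.96).

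| b | n = 40 | n = 50 |
|---|---|---|
| 0 | 5.0% | 5.0% |
| 0.1 | 9.7% | 10.9% |
| 0.2 | 24.4% | 29.3% |
| 0.3 | 47.5% | 56.4% |

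For example, with b = 0.1 and n = 40, b√n = 0.632, so the rate is Φ(−1.328) + Φ(−2.592) = 0.097. The table applies to a rater who consistently favours one vehicle. A rater who scores towards equality would not raise the false-positive rate but would hide a true difference. The plan gives no standard deviation for the IGA difference, so the two illustrations cannot be linked.

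**What a recorded guess could show**

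With one guess per child and half of them correct, the 95% half-width is 1.96 × √(0.5 × 0.5 / n):
- n = 40: 0.155
- n = 50: 0.139

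That is about ±14 to 16 percentage points.

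**The case against.** The strongest reply is that the physical cue is not in the documents. Residue is never mentioned. The Hypothesis section speaks of emulsion type and patient preference, not of what remains on skin after a wet wrap. This stands, and it limits the point to a blind that can fail.

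Several stronger readings are tempting and are not supported:
- A reader might infer that treatment is still running at the visit and that a child could arrive freshly treated. The plan gives no application frequency, last-application time or stopping point, and it calls the follow-up rating an after-treatment one. The supportable statement is that the interval is unspecified.
- A reader might infer that this trial's raters are split over the vehicle. The plan reports controversy in general; the only position it gives for the team is that the difference will be negligible.
- A reader might infer that residue alters a dryness score. Methods lists erythema, lichenification, swelling, excoriation and subjective symptoms; dryness is not listed.
- A reader might infer that the photographs fail as a blinded record. The plan gives them no such role. It says only that they are taken.
- A reader might conclude that the comparison is effectively open-label. That would need evidence of recognition in most children, and there is none.

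It is also fair to say that other routes are more evident in the text. Families know the allocation and are asked which side did better, and the medication is weighed around visits. Those routes are separate; closing them would leave the physical one open, and the reverse is also true.

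**Conclusion.** The point holds as a gap in the plan. The blind is claimed on the strength of measures that conceal the code, while the products differ, sit on opposite limbs of the same child, and are assessed in person with no stated preparation of the limbs and no check of the blind. If product is visible or palpable at the examination, the left-right IGA comparison can be biased towards or away from a difference.

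The size is unknown. The range of 0.10 to 0.35 IGA point rests on an assumed half-point shading, assumed recognition rates of 20% and 70%, and shading in one direction only; raters who lean in different directions would partly cancel. The false-positive rates likewise rest on an assumed bias. They show that even a small consistent bias matters with 40-50 children. They do not show that such a bias will occur. This is an inexpensive improvement to the main comparison, not a demonstrated failure of the trial.

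**What to change.** Write the following into the follow-up visit before enrolment starts:

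1. In the nurse part of the visit, before the physician enters and before photographs, clean and dry both limbs by one fixed procedure, with the same method and duration on each side. Then keep a fixed wait before scoring. The procedure should be fixed rather than continued until no product can be found: if ointment clings more, that limb would be rubbed longer, and the added redness would fall on a scored item.
2. After the IGA is recorded, have the physician write down which limb they think received ointment, with a don't-know option, and the reason: residue, disclosure by the family, or perceived response. The reason is needed because a rater who believes that ointment is more potent may guess from the outcome alone.
3. Report the proportion correct with its 95% interval as descriptive support. A pass/fail rule around 50% is not usable, given the interval of about ±14 to 16 points and the influence of perceived response on guesses.
4. Describe the trial as assessor-blind by intent, with that result beside the description.

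The cost is a few minutes in a visit already planned and a short addition to the form. Wiping may cause brief redness; applying it equally and waiting before scoring limits this. The change closes only the physical route. Disclosure by families and the assessor's exposure to the weighed medication need their own instructions.
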